## 5.3. Procedures for Maintaining and Breaking the Masking

The identity of the study lenses will be masked to the subjects by over labeling the blister pack of the study lens. The label will contain the study number, lot number, sphere power, expiration date and the randomization codes S and N.

The test articles mask shall not be broken unless information concerning the lens type is necessary for the urgent medical treatment of a subject. The Sponsor must be notified before the mask is broken.

When dispensing test articles, the following steps should be followed to maintain randomization codes:

- 1. Investigator or designee (documented on the Delegation Log) will consult the lens fitting schedule/randomization scheme to obtain the test article assignment for that subject prior to dispensing
- 2. Investigator or designee will record the subject's number on the appropriate line of the randomization scheme
- 3. Investigator or designee will pull the appropriate test articles from the study supply. All test articles that are opened, whether dispensed (placed/fit on eye or dispensed outside the clinical site) or not, must be recorded on the Test Article Accountability Log in the "Dispensed" section

Subjects who have had their treatment assignment unmasked are expected to return for all remaining scheduled evaluations. Subjects who are discontinued may be replaced.

## 6. STUDY INTERVENTION

## 6.1. Identity of Test Articles

The following contact lenses will be used in this study:

## Table 1: Test Articles

	Test	Control
Name	ECL100	ACUVUE OASYS
Manufacturer	JJV	JJV
Lens Material	senofilcon A	senofilcon A
Nominal Base Curve @ 22 °C	8.4	8.4
Nominal Diameter @ 22 °C	14.0	14.0
Nominal Distance Powers (D)	-1.00 through -4.50	-1.00 through -4.50
Water Content (Optional)	38	38
Center Thickness (Optional)	0.085	0.070
Oxygen Permeability (Dk)	103	103
Wear Schedule in Current Study	Daily	Daily
Replacement Frequency	Daily	Daily
Packaging Form (vial, blister, etc.)	Blister	Blister
Other distinguishing items (e.g., dye, packaging solution, optical design, etc.)	New UV/HEV blocker	NA

Approximately 25 lenses per stock keeping unit (SKU) will be provided based on 66 subjects, 2-periods, contralateral, non-dispensing design, US population normalized for peak SKUs and a safety factor of 50%.

## 6.2. Ancillary Supplies/Products

The following solutions will be used in this study:

## **Table 2: Ancillary Supplies**

[figure not shown]
	Solution
Solution Name/Description	EyeCept Rewetting Drops
Manufacturer	Optics Laboratories
Preservative	NA

## 6.3. Administration of Test Articles

Test articles will be dispensed to subject meeting all eligibility requirements, including any dispensing requirements set forth in this clinical protocol. Subjects will be dispensed an adequate supply of test articles to complete the study. Lost or damaged test articles may be replaced at the discretion of the Investigator and/or the Sponsor.

## 6.4. Packaging and Labeling

The test articles will be packaged in blisters as the primary packaging. The test article will be over-labeled to mask the subject to the identity of the lens. The test articles will be in investigational cartons sealed with a tamper evident seal, commercial cartons, or in plastic bags as the secondary packaging form. The sample study label is shown below:

## 6.5. Storage Conditions

Test articles will be maintained at ambient temperatures at the clinical site. Test articles must be kept under secure conditions and stored out of direct sunlight or other source of UV/HEV radiation.

## 6.6. Collection and Storage of Samples

When possible, any lens or test article associated with an Adverse Events and/or a Product Quality Complaint must be retained and stored in a glass vial with moderate solution pending directions from the sponsor for potential return back to JJVC.

## 6.7. Accountability of Test Articles

JJVC will provide the Investigator with sufficient quantities of study articles and supplies to complete the investigation. The Investigator is asked to retain all lens shipment documentation for the test article accountability records.

Test article must be kept in a locked storage cabinet, accessible only to those assigned by the Investigator for dispensing. The Investigator may delegate this activity to authorized study site personnel listed on the Site Delegation Log. All test articles must be accounted. This includes:

- 1. What was dispensed for the subject for trial fitting, to wear out of the office, or issued for the subject to replace appropriately between visits
- 2. What was returned to the Investigator unused

3. The number and reason for unplanned replacements

The Investigator will collect all unused test articles from the subjects at the end of the subject's participation. Subject returned unused test articles must be separated from the clinical study inventory of un-dispensed test articles, and must be labeled with the subject number and date of return. Following final reconciliation of test articles by the monitor, the Investigator or monitor will return all unused test articles to JJVC.

If there is a discrepancy between the shipment documents and the contents, contact the study monitor immediately.

Site Instructions for Test Article Receipt and Test Article Accountability for additional information.

#### 7. STUDY EVALUATIONS

#### 7.1. Time and Event Schedule

#### Table 3: Time and Events

Visit Information	Visit 1	Visit 2
	Screening, Baseline 1,	Baseline 2,
	Psychometric Testing A	Psychometric Testing B
Time Point	Day 1	1-28 Days after Visit 1
Estimated Visit Duration	2.5 hours	2.5 hours
Statement of Informed Consent	Х	
Demographics	х	
Medical History/Concomitant	v	Y
Medications	Х	Х
Habitual Contact Lens Information	Х	
Inclusion/Exclusion Criteria	х	
Baseline Questionnaires	х	
Entrance Visual Acuity	х	Х
Subjective Sphero-Cylindrical		
Refraction	Х	
Slit Lamp Biomicroscopy	х	Х
Lens Selection	х	Х
Lens Insertion & Settling	х	Х
Visual Acuity and Over Refraction	х	Х
Lens Power Modification (if		
applicable)	Х	Х
Subject Reported Ocular Symptoms	х	Х
Lens Fit Assessment	х	Х
Snellen Distance Visual Acuity	Х	Х
Study Assessments (dysphotopsia		
and/or psychophysical testing)	Х	Х

Visit Information	Visit 1	Visit 2
	Screening, Baseline 1,	Baseline 2,
	Psychometric Testing A	Psychometric Testing B
Time Point	Day 1	1-28 Days after Visit 1
Estimated Visit Duration	2.5 hours	2.5 hours
Post-assessment Questionnaire	Х	Х
Study Completion		х

## 7.2. Detailed Study Procedures

## VISIT 1

Subjects must enter Visit 1 wearing their own contact lenses.

	Visit 1: Screening			
Step	Procedure	Details		
1.1	Statement of Informed Consent	Each subject must read, understand, and sign the Statement of Informed Consent before being enrolled into the study. The Principal Investigator or his/her designee conducting the informed consent discussion must also sign the consent form. Note : The subject must be provided a signed		
		copy of this document.		
1.2	Demographics	Record the subject's year of birth, gender, race and ethnicity.		
1.3	Medical History and Concomitant Medications	Questions regarding the subjects' medical history and concomitant medications.		
1.4	Habitual Lenses	Questions regarding the subject's habitual lens type and parameters.		
1.5	Eligibility after Screening	All responses to Screening Inclusion Criteria questions must be answered "yes" and all responses to Exclusion Criteria must be answered "no" for the subject to be considered eligible. If subject is deemed to be ineligible after screening, proceed to Final Evaluation and complete Subject Disposition. Refraction and Biomicroscopy forms are not required.		

		Visit 1: Baseline	
Step	Procedure	Details	
1.6	Baseline Questionnaire	In order to determine how light sensitive participants in the study are at baseline, participants will be administered several questions from various validated instruments that measure self-reported light sensitivity.	
1.7	Entrance Visual Acuity	Record the distance Snellen visual acuity (OD, OS, and OU) to the nearest letter with their habitual contact lens correction in place. Subjects must read the smallest line until at least 50% of the letters are read incorrectly.	
1.8	Remove Habitual Lens	If applicable, the subject's habitual contact lenses will be removed and stored in their own lens case. If they forgot to bring their lens case, one will be provided to them.	
1.9	Subjective Sphero- cylindrical Refraction	Perform subjective best sphere refraction with a phoropter (adopt the maximum plus to maximum visual acuity (MPMVA) approach and use a balancing technique (e.g., the duo- chrome test for binocular balancing, or the binocular blur balancing test, etc.,) and record the best corrected distance visual acuity (OD, OS, and OU) to the nearest letter.	
1.10	Eye Dominancy	The investigator will determine eye dominancy of the subject by first using the +1.00 blur test. If this fails to determine dominancy, then the sighting test will be used. See Appendix E.	Appendix E
1.11	Slit Lamp Biomicroscopy	FDA Slit Lamp Classification Scale will be used to grade the findings and determine eligibility. If any of these slit lamp findings are grade 3 or higher, the subject may not continue at this time, but may return up to one additional time to determine eligibility. If discontinued a final examination must be completed. If the clearance of the fluorescein needs to be expedited, preservative-free rewetting drops or saline may be instilled.	

		Visit 1: Baseline	
Step	Procedure	Details	
1.12	Iris Color	The investigator will record the subject's iris color based on the scale provided (Appendix F).	Appendix F
1.13	Eligibility after Baseline	All responses to Inclusion Criteria questions must be answered "yes" and all responses to Exclusion Criteria questions must be answered "no" for the subject to be considered eligible. If subject is deemed to be ineligible after two baseline attempts at Visit 1, proceed to Final Evaluation and complete all forms.	
1.14	Lens Selection	Assign the study lens based on the randomization scheme. Select the contact lens power based on the refraction. Record the test condition.	
1.15	Lens Insertion	The Investigator or the subject inserts the study lenses. Record the time of lens insertion. Check for lens damage under the slit lamp before proceeding with lens settling. Replace damaged lenses if applicable.	
1.16	Lens Settling 1	Allow the study lenses to settle for a minimum of 5 minutes.	
1.17	Subjective Best Sphere Over Refraction	Perform subjective best sphere refraction over the study lenses (adopt the maximum plus to maximum visual acuity (MPMVA) approach.	
1.18	Lens Power Modification (if applicable)	Adjust the lens power if the subject's best sphere over-refraction is not plano. For any power modification, repeat steps (1.15-1.17). One power modification is allowed.	
1.19	Lens Settling 2	Please wait a total of 10 minutes from final lens insertion to continue.	
1.20	Subject Reported Ocular Symptoms	Subjects will respond to a verbal open-ended symptoms questionnaire.	

		Visit 1: Baseline	
Step	Procedure	Details	
1.21	Visual Acuity	Record the best corrected Snellen distance visual acuity to the nearest letter (OD and OS). Subjects must read the smallest line until at least 50% of the letters are read incorrectly.	
1.22	Subjective Lens Fit Assessment	
 
Evaluate overall lens fit acceptance (acceptable or unacceptable) based on centration, movement and other fitting characteristics.
 
An unacceptable fit is deemed by one of the following criteria: 
 
limbal exposure at primary gaze or with extreme eye movement
 
edge lift
 
excessive movement in primary and up gaze
 
insufficient movement in all three of the following conditions: primary gaze, up gaze, and Josephson push up
 
 
 
Note: if lens fit is unacceptable subject will be discontinued from the study.
 
	
1.23	Continuance	
 
For the subject to continue in the study, they must meet all three of the following criteria:
 
1. Visual acuity is 20/30 or better OD and OS
 
2. The lens fit is acceptable OD and OS
 
3. Investigator approval.
 
If the Investigator does not approve the wearing of the study lenses for the psychophysical testing, then the study is terminated for that subject.
 
	
1.24	Lenses Worn in Clinic	
 
The lenses will be released for approximately two hours.
 
1. The subjects must wear both study lenses the entire time.
 
2. The lenses will be worn as daily wear only.
 
3. Rewetting drops are permitted if needed.
 
	

	Visit 1: Baseline			
Step	Procedure	Details		
		Note:In the event a lens is lost or damaged, itwill be replaced immediately.Note:A clinic-only-wear Patient InstructionGuide will be provided.		
1.25	Psychophysical Testing Sequence	At Visit 1, all subjects will proceed to Psychophysical Testing A: This includes photostress recovery, discomfort glare, disability glare, and heterochromatic contrast in the absence of an activating light source. Following the psychometric testing by the co- investigator, the subject will return to the principal investigator to complete the study visit as described in steps 1.26-1.28.		
1.26	Lens Removal	The worn study lenses will be removed and discarded.		
1.27	Exit Slit Lamp Biomicroscopy	
 
FDA Slit Lamp Classification Scale will be used to grade the findings and determine eligibility.
 
Ocular adverse events shall be those that grade 3 or 4 on the FDA scale. The study monitored must be notified immediately. The AE will be followed to resolution at which time the subject will be terminated from the study.
 
If the clearance of the fluorescein needs to be expedited, preservative-free rewetting drops or saline may be instilled.
 
		
1.28	Exit VA	Record subjects' distance Snellen visual acuity, OD, OS, and OU to the nearest letter with their habitual correction in place (spectacles or contact lenses). Schedule Visit 2 at least 24 hours and no more than 28 days from now.		

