# FINAL EVALUATION

The final evaluation will ordinarily take place immediately following the last scheduled follow-up visit per the study protocol. It may also take place at any point the subject discontinues the study or is terminated from the study.

Final Evaluation			
Step	Procedure	Details	
F.1	Final Exam Form	Indicate if the subject completed the study successfully. If subject discontinued from the study, indicate the reason.	
F.2	Subjective spherocylindrical Refraction	Perform bare-eye subjective spherocylindrical refraction with a phoropter and record the best corrected distance visual acuity to the nearest letter (OD, OS, and OU).	

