- Permanent decrease in best spectacle corrected visual acuity equivalent to 2 acuity lines or greater
- Central Corneal Opacity
- Central Corneal Neovascularization

- Uveitis
- Endophthalmitis
- Hypopyon
- Hyphemia
- Penetration of Bowman's Membrane
- Persistent Epithelial Defect
- Limbal cell Damage leading to Conjunctivalization

**Significant Adverse Events** – Those events that are usually symptomatic and warrant discontinuation (temporary or permanent) of the test article (excluding Serious Adverse Events).

Diagnoses and conditions that are considered Ocular Significant Adverse Events include, but not limited to the following:

- Contact Lens Induced Peripheral Ulcer (CLPU)
- Significant Infiltrative Events (SIE)
- Superior Epithelial Arcuate Lesions (SEALs)
- Any Temporary Loss of > 2 Lines of BSCVA
- Other grade 3 or higher corneal findings, such as abrasions or edema
- Non-contact lens related corneal events e.g. Epidemic Keratoconjunctivitis (EKC)
- Asymptomatic Corneal Scar
- Any corneal event which necessitates temporary lens discontinuation > 2 weeks

**Non-Significant Adverse Events** – Those conditions that are usually asymptomatic and usually do not warrant discontinuation (temporary or permanent) of the test article. However, the Investigator may choose to treat as a precautionary measure.

Diagnoses and conditions that are considered Ocular Non-Significant Adverse Events include, but not limited to the following:

- Non-significant Infiltrative Event (NSIE)
- Contact Lens Papillary Conjunctivitis (CLPC)
- Superficial Punctate Keratitis (SPK)
- Conjunctivitis: Bacterial, Viral, Allergic
- Blepharitis
- Meibomianitis
- Contact Dermatitis
- Localized Allergic Reactions
- Any corneal event not explicitly defined as serious or significant adverse event, which necessitates temporary lens discontinuation < 2 weeks

Adverse Device Effect (ADE) – An ADE is an "adverse event related to the use of an investigational medical device.

*Note 1* to entry: This definition includes adverse events resulting from insufficient or inadequate instructions for use, deployment, implantation, installation, or operation, or any malfunction of the investigational medical device.

*Note 2* to entry: This definition includes any event resulting from use error or from intentional misuse of the investigational medical device."

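### Step 1.9 contradicts itself on the baseline refraction (titled spherocylindrical, instructed best sphere); followed literally, it can understate later acuity loss and leaves the eye-dominance test without its input.

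*Combined protocol and SAP*

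**What the plan says.** Section 7.2, Visit 1 step 1.9 carries a sphero-cylindrical title. Its instruction is "Perform subjective best sphere refraction with a phoropter (adopt the maximum plus to maximum visual acuity (MPMVA) approach", followed by a balancing technique, after which the site must "record the best corrected distance visual acuity (OD, OS, and OU) to the nearest letter". The instruction does not mention cylinder.

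Other places describe the baseline refraction differently or depend on it:

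- Table 3 lists the procedure as "Subjective Sphero-Cylindrical" refraction, at Visit 1 only.
- The Appendix D procedure heading also says spherocylindrical. Its pages are not reproduced in the public text.
- Step 1.10 sends the site to Appendix E, whose first test starts by placing the subject's sphero-cylindrical distance refraction in a trial frame.

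The later measurements name the method clearly. Final Evaluation step F.2 says "Perform bare-eye subjective spherocylindrical refraction with a phoropter and record the best corrected" distance acuity. Step U.4 (section 7.3) opens the same way, and section 8.2 asks for a spherocylindrical refraction with best corrected acuity in discontinued subjects.

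Section 13.1 lists as an ocular serious event "Permanent decrease in best spectacle corrected visual acuity equivalent to 2 acuity lines or greater" and as an ocular significant event "Any Temporary Loss of > 2 Lines of BSCVA".

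**The concern.** Both section 13.1 definitions are changes from a baseline, so baseline and follow-up must be measured in the same way. Apart from measurement noise, leaving cylinder uncorrected can only lower the recorded baseline or leave it unchanged. Correcting it later has the opposite effect. If step 1.9 is carried out as instructed, the error therefore runs one way, towards no loss.

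Step 1.9 is the only bare-eye best corrected acuity at baseline. Visit 2 ends with lens removal and slit lamp (steps 2.18 and 2.19) and has no exit acuity. For completers, F.2 is therefore the only acuity taken after the Visit 2 lenses come off, and step 1.9 is its natural comparator.

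What is at stake is the classification and timing of safety reports. Under section 13.4, serious and significant events reach the sponsor within 24 hours and non-significant events within 2 days. Separately, the first dominance test would lack its stated input.

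**Working it through.** The plan gives no figure on this point, so there is none to reproduce. The check is a comparison of passages followed by a simple illustration.

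**Refraction by time point**

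| Place | Method in the text | Acuity recorded |
|---|---|---|
| Step 1.9, title | sphero-cylindrical | – |
| Step 1.9, instruction | best sphere | best corrected, each eye and both |
| Table 3 | sphero-cylindrical, Visit 1 only | – |
| Appendix E step 1 (used in step 1.10) | needs a sphero-cylindrical result | – |
| F.2, final evaluation | spherocylindrical | best corrected |
| U.4, unscheduled visit | spherocylindrical | best corrected |
| Section 8.2, discontinued subjects | spherocylindrical | best corrected |
| Section 13.3, event discovery and conclusion | not stated | best corrected |

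The step 1.9 instruction is the only entry that names best sphere for a bare-eye refraction. The protocol also uses that term for the over-refraction at steps 1.17 and 2.9, a separate measurement through the study lenses.

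**Illustration if the instruction is followed literally**

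Let m be the number of lines by which best-sphere acuity falls short of spherocylindrical acuity at baseline. Then

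recorded loss = true loss − m.

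The documents give no cylinder data, so m is an assumption, taken from 0 to 2 lines. Acuity is recorded to the nearest letter, so fractions of a line can occur.

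| m (assumed) | True 2-line permanent loss: recorded; serious trigger (2 or more) | True 3-line temporary loss: recorded; significant trigger (more than 2) |
|---|---|---|
| 0 | 2 − 0 = 2; met | 3 − 0 = 3; met |
| 0.5 | 2 − 0.5 = 1.5; missed | 3 − 0.5 = 2.5; met |
| 1 | 2 − 1 = 1; missed | 3 − 1 = 2; missed |
| 1.5 | 2 − 1.5 = 0.5; missed | 3 − 1.5 = 1.5; missed |
| 2 | 2 − 2 = 0; missed | 3 − 2 = 1; missed |

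Larger losses are more robust. A true 4-line temporary loss is still caught at m = 1.5 (4 − 1.5 = 2.5) and is missed only at m = 2 (4 − 2 = 2, which is not more than 2).

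**Is such an m compatible with entry?** Inclusion criterion 6 requires 20/25 or better in each eye. In logMAR, 20/25 is 0.097, 20/20 is 0 and 20/16 is −0.097, so each step is about one line. An eye at the 20/25 floor with best sphere would have m = 1 if full correction gives 20/20, and m = 2 if it gives about 20/16. The entry rule therefore permits the range but says nothing about how often it occurs.

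**With one method throughout,** m = 0 and recorded loss equals true loss.

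**The case against.** The strongest reply is that this is a wording slip. The title, Table 3, the Appendix D heading and Appendix E all point to a spherocylindrical refraction, and step 1.10 cannot be done as written without one. A site that follows the title has no mismatch. This stands: a reader might infer that the sponsor chose a best-sphere baseline, and the documents do not support that. They support a contradiction that permits either reading.

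Other measures give some protection:

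- Subjects enter both visits in their own contact lenses, so acuity at steps 1.7 and 2.2 is like for like, and a 2- to 3-line loss persisting from Visit 1 should show there. It is not the spectacle-corrected measure named in section 13.1, however, and step 2.2 comes before the Visit 2 lenses are worn.
- Section 13.3 asks for best corrected acuity at both discovery and conclusion of an event, so a temporary loss can partly be judged within the event.
- Slit lamp findings trigger events independently, and the medical monitor takes part in categorisation.

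The size is also bounded. Toric wearers are excluded, subjects must be current spherical-lens wearers, and each eye must reach 20/30 in spherical study lenses to continue. None of these sets a cylinder limit, but together they restrict its visual cost.

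Two further inferences should be resisted. One is that inclusion criterion 5 cannot be assessed: a best sphere can approximate the spherical equivalent, even though the cylinder goes unrecorded. The other is that step 1.28 must change because it allows acuity "with their habitual correction in place (spectacles or contact lenses". Habitual-correction acuity is not the measure in either section 13.1 threshold.

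**Conclusion.** The point holds as an internal contradiction with a conditional safety consequence. If the step 1.9 instruction is followed and the eye has meaningful cylinder, the baseline is understated relative to F.2, U.4 and discontinuation, and a later loss can be under-recorded against section 13.1. Under that reading, an assumed shortfall of 1 line is enough for a true 2-line permanent loss and a true 3-line temporary loss each to miss its threshold. With no shortfall, nothing is missed.

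The number of eyes affected cannot be estimated from the documents. Acuity-loss events should be rare after about two hours of wear per visit, so few or no subjects may be affected.

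A reader might also infer that the efficacy results are compromised, because dominant eye is a fixed effect in the primary and secondary models (sections 14.5 and 14.6). The documents do not support that. They show only that the input to the first dominance test is not produced by the instruction as worded, and any numerical effect on the lens comparison is probably small.

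**What to change.** Reconcile step 1.9 with its title by using the refraction wording of step U.4, which opens "Perform bare-eye subjective spherocylindrical refraction with a phoropter", and keep the recording of best corrected acuity for each eye and both eyes. State in section 13.1 that this acuity is the baseline for both acuity-loss definitions.

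This also supplies the input that Appendix E needs. The procedure is already named in the step title, listed in Table 3 and covered by an Appendix D heading, so the cost is rewording one step and adding one sentence, with at most a minute or two more chair time where a site had been doing best sphere only. No change to step 1.28 or to criterion 5 is needed for this point.

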## **13. ADVERSE EVENTS**

#### 13.1. Definitions and Classifications

Adverse Event (AE) – An AE is "any untoward medical occurrence, unintended disease or injury, or untoward clinical signs (including abnormal laboratory findings) in subjects, users or other persons, whether or not related to the investigational medical device.

*Note 1* to entry: This definition includes events related to the investigational medical device or the comparator.

Note 2 to entry: This definition includes events related to the procedures involved.

*Note 3* to entry: For users or other persons, this definition is restricted to events related to investigational medical devices."

An AE includes any condition (including a pre-existing condition) that:

- 1. Was not present prior to the study, but appeared or reappeared following initiation of the study
- 2. Was present prior to the study, but worsened during the study. This would include any condition resulting from concomitant illnesses, reactions to concomitant medications, or progression of disease states
- 3. Pregnancy must be documented as an adverse event and must be reported to the clinical monitor and to the Sponsor immediately upon learning of the event

Serious Adverse Event (SAE) – An SAE is any untoward medical occurrence that:

- Results in death
- Is life threatening
- Requires in-patient hospitalization or prolongation of existing hospitalization
- Results in persistent or significant disability/incapacity (e.g., a sight threatening event, a significant persistent or permanent change, impairment, damage, or disruption to the subject's body)
- Is a congenital anomaly/birth defect
- Requires intervention to prevent permanent damage (the use of the test article resulting in a condition which requires medical or surgical intervention to preclude permanent impairment of the body structure or a body function). Important medical events that may not result in death, be life-threatening, or require hospitalization may be considered an SAE when, based upon appropriate medical judgment, they may jeopardize the patient or subject and may require medical or surgical intervention to prevent one of the outcomes listed in the above definition

Diagnoses and conditions that are considered Ocular Serious Adverse Events include, but not limited to:

- Microbial Keratitis (MK)
- Iritis (including cells in the anterior chamber)

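### The exit slit-lamp steps limit ocular adverse events to grade 3 or 4 findings, whereas Section 13.1 lets an untoward new or worsened finding of any grade be an adverse event

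*Combined protocol and SAP*

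**What the plan says.** Section 7.2 uses the same sentence at the exit examination of Visit 1 (step 1.27) and Visit 2 (step 2.19): "Ocular adverse events shall be those that grade 3 or 4 on the FDA scale". Both steps then require immediate notification of the study monitor. Step 1.27 adds: "The AE will be followed to resolution at which time the subject will be terminated from the study". Step 2.19 asks for follow-up to resolution but does not mention termination.

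The pre-insertion examinations (steps 1.11 and 2.4) use the same grade as a gate: "If any of these slit lamp findings are grade 3 or higher, the subject may not continue at this time".

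Section 13.1 defines an AE broadly. Untoward clinical signs are included, whether or not they are related to the device. Among the conditions covered are one that "Was not present prior to the study, but appeared or reappeared following initiation of the study" and one that "Was present prior to the study, but worsened during the study". Ocular AEs are then sorted into Serious, Significant and Non-Significant classes. Grade appears in one entry of the Significant class: "Other grade 3 or higher corneal findings, such as abrasions or edema". The Non-Significant class has nine entries, among them superficial punctate keratitis and contact lens papillary conjunctivitis, and none carries a grade.

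Section 13.2 calls for a causality assessment of each AE. Section 13.3 requires every AE during enrolment to be documented and leaves continuation to the investigator's judgment. Section 13.4.1 gives 2 days to report non-serious AEs to the sponsor. Section 14.7 plans a descriptive summary of slit-lamp findings by lens type.

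**The concern.** The sentence in the exit steps is worded as a definition. It does not say that grade 3 or 4 findings are always AEs, or that they are the ones needing urgent notification. It says that ocular AEs are those findings. Section 13.1 would admit some findings that this sentence shuts out, and nothing in the protocol ranks the two.

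The location matters. These are the only scheduled slit-lamp examinations directly after study-lens wear. The Final Evaluation lists only a disposition form and a refraction. Step 2.4 takes place 1 to 28 days after Visit 1, with subjects arriving in their own lenses. The examiner at exit is likely to work from the procedure table.

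At stake is the completeness and consistency of the AE record for an investigational lens. Two examiners seeing the same eye could reach different answers depending on which section they follow.

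**Working it through.** There is no figure in the plan to reproduce. The check compares the two rules on the same findings.

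**Starting grade.** Steps 1.11 and 2.4 hold back any subject at grade 3 or higher, so eyes that receive a study lens start below grade 3. Two things follow. A finding of grade 3 or 4 at exit is necessarily new or worse than at that visit's pre-insertion examination. A finding can also appear or worsen and still end below grade 3.

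**Four illustrative exit findings under each rule:**

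- *Grade 3 or 4 at exit.* Steps 1.27 and 2.19: AE. Section 13.1: new or worsened, and where corneal it falls in the Significant class. No conflict.
- *Staining absent at step 1.11, grade 2 at exit, judged untoward.* Exit steps: not an ocular AE. Section 13.1: an AE. **Conflict.**
- *Finding at grade 1 at step 1.11, grade 2 at exit, judged untoward.* Exit steps: not an ocular AE. Section 13.1: a worsened condition, hence an AE. **Conflict.**
- *The same change from 1 to 2, judged not untoward.* Exit steps: not an AE. Section 13.1: not an AE. No conflict.

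The rules therefore diverge for findings that end below grade 3, are new or worse, and are judged untoward.

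**Consequence where they diverge.** If the exit steps are followed, the finding is not entered as an AE (Section 13.3), its causality is not assessed (Section 13.2) and the 2-day report is not made (Section 13.4.1). Its grade can still reach the summary in Section 14.7.

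**Scope of the rule.** Eye-examinations at exit = subjects × eyes × exit examinations:

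- 60 completers: 60 × 2 × 2 = 240
- all 66 enrolled attending both visits: 66 × 2 × 2 = 264

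This counts how often the rule is applied. It does not count affected findings.

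**Comparator for new or worse.** Section 13.1 looks back to before the study, which is step 1.11. Using only step 2.4 at Visit 2 would miss a finding that was worse at 2.4 than at 1.11 and unchanged at exit. Using only 1.11 would miss one that had cleared by 2.4 and returned at exit, which Section 13.1 treats as reappearing. Visit 2 needs both.

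**Link to the termination sentence.** If the AE definition in step 1.27 is widened and the sentence ending participation is left alone, every lower-grade AE at the Visit 1 exit would end participation. All three primary endpoints are measured at Visit 2 (Section 2.2). The two sentences must be changed together.

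**The case against.** The strongest defence is that the sentence follows directly on the instruction to grade findings with the FDA scale. It may be meant only as the cut-off at which a graded sign counts as an AE in itself. On that reading the Non-Significant entries are mainly diagnoses, which Section 13.3 asks for in preference to symptoms, and they go through Section 13 without a grade. Section 13 also continues to operate. The investigator and medical monitor categorise events under 13.2, all AEs must be documented under 13.3, and step 2.1 and the unscheduled-visit form collect AEs with no grade limit. The biomicroscopy scale in Appendix D is not visible in the text available and might bear on how low grades are handled.

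This reading does not remove the conflict. Section 13.1 expressly includes untoward clinical signs and worsened conditions, so graded signs fall under it as well as diagnoses. Neither the AE review at step 2.1 nor the summary in 14.7 is stated to override the exit sentence. What Appendix D says cannot be checked.

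Part of the defence stands. A reader might infer that Section 13.1 makes every worsening below grade 3 an AE, so that every extra form is already mandatory. The documents do not support that, because the definition needs a judgment that the sign is untoward. The subjects are habitual soft-lens wearers, entry is barred only at grade 3 or above, and wear is about two hours per visit. Some low-grade change may reasonably be judged unremarkable.

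**Conclusion.** The inconsistency is real and is present at both visits. Its effect is limited to safety recording: a lower-grade finding that meets Section 13.1 could go unrecorded, unassessed for causality and unreported within 2 days. This assumes that the examiner follows the procedure step literally and that such a finding occurs and is judged untoward.

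A reader might also infer that a material share of AEs will be lost, or that the lens comparison is affected. The documents support neither. They give no rate of low-grade findings, so the 240 to 264 eye-examinations describe scope only. Slit-lamp findings are still summarised by lens type, and none of the primary or secondary efficacy analyses uses AE status. Severity is minor.

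**What to change.** In steps 1.27 and 2.19 replace the definitional sentence, and the monitor-notification sentence after it, with:

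> Grade 3 or 4 findings are always recorded as AEs, with immediate notification of the study monitor. Any other ocular finding that is new or worse than the Visit 1 pre-insertion examination (step 1.11), or at Visit 2 also than step 2.4, is assessed under Section 13.1 and recorded as an AE if the investigator judges it untoward.

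In step 1.27 limit the sentence on follow-up to resolution and termination to grade 3 or 4 AEs. Continuation after a lower-grade AE then stays with the investigator's judgment under Section 13.3, and the wider recording does not force withdrawals before Visit 2.

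The cost is wording in two steps and a few more AE assessments and forms. No examinations, subjects or discontinuation rules are added. Because one-grade differences can reflect ordinary grading variation, some assessments will end with no AE recorded; the untoward judgment is there to sort these.
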